9.3.2 Outcomes

9.3.2.1 Primary outcomes

The primary outcome is whether patient has Cardiac arrhythmias on the index date or in the year prior to the index date. Cardiac arrhythmias is defined as having the following readcode in the above mentioned time period:

medcode	readcode	readterm
17597	327..00	ECG: supraventricular arrhythmia
19707	328..00	ECG: ventricular arrhythmia
29371	328Z.00	ECG: ventricular arrhythmia NOS
97780	G559.00	Arrhythmogenic right ventricular cardiomyopathy
6503	G57..11	Cardiac arrhythmias
426	G577.00	Sinus arrhythmia
31690	G57yA00	Re-entry ventricular arrhythmia
53893	Gyu5a00	[X]Other specified cardiac arrhythmias
26670	2432.00	O/E - pulse irregularly irreg.
18746	662S.00	Atrial fibrillation monitoring
45773	6A9..00	Atrial fibrillation annual review

Protocol for non-interventional studies based on existing data

BI Study Number 0205-0537

c25002535-01

Proprietary confidential information © 2018 Boehringer Ingelheim International GmbH or one or more of its affiliated companies

9479	7936A00	Implant intravenous pacemaker for atrial fibrillation
92361	793M000	Perc translum ablat pulmon vein to lft atrium conduct system
105554	8CMW200	Atrial fibrillation care pathway
57832	9Os..00	Atrial fibrillation monitoring administration
90187	9Os0.00	Atrial fibrillation monitoring first letter
90188	9Os1.00	Atrial fibrillation monitoring second letter
90189	9Os2.00	Atrial fibrillation monitoring third letter
90190	9Os3.00	Atrial fibrillation monitoring verbal invite
90191	9Os4.00	Atrial fibrillation monitoring telephone invite
63350	9hF..00	Exception reporting: atrial fibrillation quality indicators
39114	9hF1.00	Excepted from atrial fibrillation qual indic: Inform dissent
2212	G573.00	Atrial fibrillation and flutter
1664	G573000	Atrial fibrillation
35127	G573300	Non-rheumatic atrial fibrillation
96277	G573400	Permanent atrial fibrillation
96076	G573500	Persistent atrial fibrillation
23437	G573z00	Atrial fibrillation and flutter NOS

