Variables:	
As stated above the patients will be grouped by type of treatment initiated or switched to. This will include Spiriva Respimat, a higher dose of ICS/LABA FDC, a new ICS/LABA FDC or an LTRA. Patient characteristics will be identified based on data recorded on the index date (date of dispensing/initiation of the exposure), or when a characteristic was not recorded on the index date, during the pre-index period (the one closest to the index date), unless otherwise specified.
 
The outcome is whether a patient has a cardiac arrhythmias diagnosis on the index date or in the year prior to the index date. The secondary outcome is whether a patient has a cardiac failure diagnosis on the index date or in the year prior to the index date.
 
In addition, the following covariates will be assessed in this study:
 
 • Demographic characteristics • Lifestyle factors • Asthma history and lab tests • Comorbidities • Concomitant prescriptions (both asthma related and non-asthma related prescriptions) 		
Data sources:	United Kingdom's Clinical Practice Research Datalink (CPRD) GOLD database		

Protocol for non-interventional studies based on existing data

BI Study Number 0205-0537

c25002535-01

Proprietary confidential information © 2018 Boehringer Ingelheim International GmbH or one or more of its affiliated companies

Name of company: Boehringer Ingelheim																																								
Name of finished medicinal product: Spiriva® Respimat®																																								
Name of active ingredient: Tiotropium bromide (ATC code R03B B04)																																								
Protocol date: 3 Aug, 2018	Study number: 0205-0537	Version/Revision: 1.0	Version/Revision date: 3 Aug, 2018																																					

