7. RATIONALE AND BACKGROUND

Asthma is a respiratory condition that causes symptoms of wheezing, shortness of breath, chest tightness and cough [[P18-03927](#)]. According to treatment guidelines, asthma patients at treatment step 3 and above should be treated with inhaled corticosteroids often in combination with long-acting beta agonists. However, many patients continue to have symptoms despite the use of these agents [[P10-08936](#)].

In late 2014, Spiriva Respimat (tiotropium), a long acting anticholinergic, was approved for treatment of asthma in the UK. Since this time, it has been approved for use in asthma patients in other countries including Japan and the United States. In the U.K., Spiriva® Respimat® is indicated as an add-on maintenance bronchodilator treatment in adult patients with asthma who are currently treated with the maintenance combination of inhaled corticosteroids ($\geq 800\mu\text{g}$ budesonide/day or equivalent) and long-acting beta2-agonists and who experienced one or more severe exacerbations in the previous year.

The current BTS/SIGN Guideline for the management of asthma recommends tiotropium by soft-mist inhaler as an alternate controller therapy at steps three, four and five of the asthma treatment paradigm, on top of inhaled corticosteroid (ICS)/LABA [[P18-03927](#)]. Alternatively, these patients could also be treated with a higher dose of ICS or ICS/LABA or MART, addition of leukotriene receptor antagonist (LTRA), addition of theophylline, beta agonist tablet, or switching to a different ICS/LABA, as shown in [figure 1](#).

Protocol for non-interventional studies based on existing data

BI Study Number 0205-0537

c25002535-01

Proprietary confidential information © 2018 Boehringer Ingelheim International GmbH or one or more of its affiliated companies

[figure not shown]

Figure 1 Summary of asthma management in adults.

Tiotropium is the first of its class approved for the use in the treatment of asthma. After a drug is launched in the market, it is important to identify patient clinical and socio-demographic characteristics of patients who initiate this treatment as opposed to other available treatments for patients at the same stage of disease. This type of study will allow us to evaluate potential channeling of prescribing to different patient populations. The results of the current study can also be used to determine the variables included in the calculation of propensity scores in future studies.

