90192	9Or2.00	Heart failure monitoring verbal invite
72965	9Or3.00	Heart failure monitoring first letter
72386	9Or4.00	Heart failure monitoring second letter
89650	9Or5.00	Heart failure monitoring third letter
21837	G232.00	Hypertensive heart&renal dis wth (congestive) heart failure
28684	G233.00	Hypertensive heart and renal disease with renal failure
57987	G234.00	Hyperten heart&renal dis+both(congestv)heart and renal fail
2062	G58..00	Heart failure
1223	G58..11	Cardiac failure
398	G580.00	Congestive heart failure
2906	G580.11	Congestive cardiac failure
10079	G580.12	Right heart failure
10154	G580.13	Right ventricular failure
9524	G580.14	Biventricular failure
23707	G580000	Acute congestive heart failure
32671	G580100	Chronic congestive heart failure
27884	G580200	Decompensated cardiac failure
11424	G580300	Compensated cardiac failure
94870	G580400	Congestive heart failure due to valvular disease
884	G581.00	Left ventricular failure
23481	G581.11	Asthma - cardiac
43618	G581.12	Pulmonary oedema - acute
5942	G581.13	Impaired left ventricular function
5255	G581000	Acute left ventricular failure
27964	G582.00	Acute heart failure
101138	G583.00	Heart failure with normal ejection fraction
101137	G583.11	HFNEF - heart failure with normal ejection fraction
106897	G583.12	Heart failure with preserved ejection fraction
104275	G584.00	Right ventricular failure
4024	G58z.00	Heart failure NOS
12590	G58z.11	Weak heart

Protocol for non-interventional studies based on existing data

BI Study Number 0205-0537

c25002535-01

Proprietary confidential information © 2018 Boehringer Ingelheim International GmbH or one or more of its affiliated companies

17278	G58z.12	Cardiac failure NOS
96799	G5y4z00	Post cardiac operation heart failure NOS
8966	G5yy900	Left ventricular systolic dysfunction
12550	G5yyA00	Left ventricular diastolic dysfunction
104876	G5yyB00	Right ventricular diastolic dysfunction
104333	G5yyC00	Diastolic dysfunction
20822	Q48y100	Congenital cardiac failure
66306	SP11111	Heart failure as a complication of care
26242	ZRad.00	New York Heart Assoc classification heart failure symptoms

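### The primary outcome is named cardiac arrhythmias but defined by a closed list of 28 codes, mostly atrial fibrillation; the name and the list need to be aligned

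*Protocol*

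**What the plan says.** Protocol section 9.3.2.1 makes the primary outcome the presence of cardiac arrhythmias on the index date or in the year before it, and operationalises it as follows: "Cardiac arrhythmias is defined as having the following readcode in the above mentioned time period". The table below that sentence is the whole definition. Its entries include "Persistent atrial fibrillation", "Re-entry ventricular arrhythmia", "Atrial fibrillation monitoring telephone invite" and "O/E - pulse irregularly irreg".

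The Abstract uses the same broad name: "The outcome is whether a patient has a cardiac arrhythmias diagnosis on the index date" (or in the preceding year). Neither place limits the outcome to AF.

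Section 9.4 describes Read as a hierarchical system but gives no rule that a listed parent code brings in its children. The linked hospital data described there serve hospitalisation and exacerbation counts, not arrhythmia. Section 9.7.1 tabulates this outcome and compares it between treatment groups by ASD, with 10% as the mark of a meaningful difference. Section 7 adds that the results "can also be used to determine the variables included in the calculation of propensity scores in future studies".

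**The concern.** The label promises a broad clinical category and the list delivers something narrower. Two chronic forms of AF are listed while paroxysmal AF is not, and no restriction is explained. The eight non-AF arrhythmia terms all share one letter string, so a rhythm disorder with any other name does not appear.

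A patient without a listed code is a non-case, not a missing value, so the separate missing category in section 9.7.3 does not help. If patients recorded only under unlisted codes are numerous, the prevalence in the report is not the prevalence of the named outcome. An ASD below 10% could then be read as no channeling on arrhythmia when the comparison mainly concerned AF. Because of the forward use described in section 7, that reading could carry into later studies.

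**Working it through.** **Step 1. Is the definition fixed here?** Yes. The sentence in 9.3.2.1 is closed: it does not say *including*, has no child-code rule and names no other source. Section 9.8 says the protocol will be strictly followed, and Annex 1 lists no stand-alone documents.

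**Step 2. Count the 28 listed terms.**
- Naming atrial fibrillation: 18 (662S, 6A9, 7936A, 8CMW2, 9Os.., 9Os0 to 9Os4, 9hF.., 9hF1, G573.00, G573000, G573300, G573400, G573500, G573z00).
- Containing *arrhythm*: 8 (327, 328, 328Z, G559, G57..11, G577, G57yA, Gyu5a).
- Pulmonary-vein ablation: 1 (793M000).
- Irregular-pulse examination sign: 1 (2432.00).
- Sum: 18 + 8 + 1 + 1 = 28.

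Terms containing tachycardia, bradycardia, block, ectopic, ventricular fibrillation or paroxysmal: 0. Flutter occurs twice, both times combined with AF.

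**Step 3. The plan's own precision figures.** Table 1 in section 9.5 is reproduced by Wilson 95% intervals in 19 of 20 cells. For example, 500 users at 5% gives 3.4–7.3. The remaining cell, 2,000 users at 10%, gives 8.8–11.4 against the printed 8.8–11.3, a last-digit difference. These intervals are sound, but they cover sampling error only, not what the list fails to capture.

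**Step 4. Illustration of scale.** The documents give no code frequencies, so the share missed, m, is an assumption: 10% to 40%, equal in both groups, with no false positives. The Spiriva group size, 935, is from section 9.5. The 5% prevalence is one of the Table 1 scenarios, used here as an assumed true value.

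- Observed prevalence = (1 − m) × p. With p = 5%: 0.9 × 5% = 4.5%; 0.6 × 5% = 3.0%.
- True cases: 935 × 0.05 = 46.75. Missed: 0.1 × 46.75 = 4.7; 0.4 × 46.75 = 18.7, so about 5 to 19 patients.
- ASD = |p1 − p0| / √{[p1(1 − p1) + p0(1 − p0)] / 2}.

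| m | p1 observed | p0 observed | ASD |
|---|---|---|---|
| 0 | 7.41% | 5.0% | 10.0% |
| 0.1 | 6.67% | 4.5% | 9.5% |
| 0.4 | 4.45% | 3.0% | 7.6% |

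Conversely, for the table to show 10% with p0 = 5%, the true p1 must be 7.56% (true ASD 10.6%) at m = 0.1, or 8.25% (true ASD 13.1%) at m = 0.4. With p0 = 2% the range is 10.6–13.0%, and with p0 = 10% it is 10.6–13.3%.

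**Step 5. Allow for false positives.** Step 4 assumes none, yet 2432.00 alone makes a case and is an examination sign. If f is the proportion of true non-cases who enter on such a code, observed prevalence = (1 − m)p + f(1 − p). This equals p when f = mp/(1 − p). With p = 5%: 0.005/0.95 = 0.53% at m = 0.1, and 0.02/0.95 = 2.1% at m = 0.4. Beyond those values the reported prevalence would be too high, not too low. The documents give neither m nor f.

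**The case against.** Five arguments on the other side deserve weight.

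- **The loss depends on a source not shown.** Patients are missed only if Read has separate codes for the unnamed rhythms and practices used those alone. The listed codes do skip positions (within G573 the entries run 0, 3, 4, 5, z), but the protocol does not say what the gaps hold. This stands. A reader might infer that the list is proven incomplete; the gaps are consistent with that and do not prove it.
- **Generic and class-level codes are listed.** These include the supraventricular and ventricular ECG codes, "Re-entry ventricular arrhythmia", the heading synonym for cardiac arrhythmias and a code for other specified arrhythmias. They capture some patients with the unnamed types. This stands, but only for patients given those exact codes.
- **The heart-failure list is no benchmark.** It is fuller under its own heading, down to entries such as "Chronic congestive heart failure", but it also holds screening and suspicion codes. A different construction there does not show an error here. This stands.
- **The scope may be deliberate.** Whether conduction block, bradycardia or ectopic beats belong is a scoping choice. It is nowhere stated, and sinus and ventricular arrhythmia are included, so an AF-only intention does not fit the list either.
- **The effect is modest against noise.** In the example the ASD moves by 0.5 to 2.4 points. With SE(p1) = √(0.0741 × 0.9259/935) = 0.86% and a pooled SD of 24.1%, sampling error is about 1.96 × 0.86/24.1 = 7 points even with an unlimited comparator group. At 10% loss, the reported 4.5% lies within the Wilson interval for 5% (3.8–6.6). Related drugs, such as antiarrhythmics and oral anticoagulants, are also compared and give a partial second view.

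Section 9.9 concedes misclassification of comorbidities and relies on using all data before the index date. That cannot recover codes absent from the list, and this outcome has a one-year window.

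**Conclusion.** The mismatch between name and definition holds on the protocol's text alone. The outcome is called cardiac arrhythmias; the list is closed, 18 of its 28 terms name AF, and several common rhythm-disorder names are absent. Anyone recorded only under an unlisted code becomes a non-case, so the prevalence and the ASD describe the list rather than the label. *Mainly AF* here refers to the make-up of the list; the mix of patients it would select is unknown.

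A reader might go further and conclude that arrhythmia prevalence is under-counted and the ASD biased towards zero. The documents do not support that. They do not show which unlisted codes exist or how often they are used, and non-diagnostic codes such as 2432.00 push prevalence the other way. The shrinkage of the ASD in the illustration also requires equal error in both groups; unequal error could move it in either direction. The 10–40% range is an assumption, not an estimate.

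The study is descriptive, and section 7 does not make the 10% cut-off a rule for choosing propensity-score variables. Even so, this is the named primary outcome and its definition is settled before extraction, so it should be corrected.

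**What to change.** Before extraction, check the list in 9.3.2.1 against the Read hierarchy and complete it for the rhythm disorders the outcome is meant to cover. State whether child codes of listed parents count, and name any arrhythmia types left out on purpose, with the reason.

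If the present list is what is wanted, rename the outcome in 9.3.2.1 and in the Abstract to what it captures: mainly AF plus selected other arrhythmia codes.

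Completing the list costs some code-list work on data already held. Renaming costs only text, but leaves the other arrhythmias undescribed, and the report should then draw no conclusion about channeling on arrhythmia in general.

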9.3.2.2 Secondary outcomes

The secondary outcome is whether patient has Cardiac failure on the index date or in the year prior to the index date. Cardiac failure is defined as having the following readcode in the above mentioned time period:

medcode	readcode	readterm
15058	14A6.00	H/O: heart failure
46912	14AM.00	H/O: Heart failure in last year
21235	1J60.00	Suspected heart failure
9913	1O1..00	Heart failure confirmed
46672	388D.00	New York Heart Assoc classification heart failure symptoms
106198	661M500	Heart failure self-management plan agreed
83502	662p.00	Heart failure 6 month review
12366	662T.00	Congestive heart failure monitoring
30779	662W.00	Heart failure annual review
95835	679X.00	Heart failure education
60099	67D4.00	Heart failure information given to patient
46636	68B6.00	Heart failure screen
105542	8CeC.00	Preferred place of care for next exacerbation heart failure
32945	8CL3.00	Heart failure care plan discussed with patient
103732	8CMK.00	Has heart failure management plan
106008	8CMW800	Heart failure clinical pathway
32898	8H2S.00	Admit heart failure emergency
17851	8HBE.00	Heart failure follow-up
91288	8Hg8.00	Discharge from practice nurse heart failure clinic
102585	8HgD.00	Discharge from heart failure nurse service
26115	8HHb.00	Referral to heart failure nurse
70619	8HHz.00	Referral to heart failure exercise programme

Protocol for non-interventional studies based on existing data

BI Study Number 0205-0537

c25002535-01

Proprietary confidential information © 2018 Boehringer Ingelheim International GmbH or one or more of its affiliated companies

71235	8Hk0.00	Referred to heart failure education group
48897	8HTL.00	Referral to heart failure clinic
106894	8IE1.00	Referral to heart failure exercise programme declined
90935	9hH..00	Exception reporting: heart failure quality indicators
30749	9hH0.00	Excepted heart failure quality indicators: Patient unsuitabl
64062	9hH1.00	Excepted heart failure quality indicators: Informed dissent
106545	9m5..00	High risk of heart failure screening invitation
12627	9N0k.00	Seen in heart failure clinic
19002	9N2p.00	Seen by community heart failure nurse
95021	9N4s.00	Did not attend practice nurse heart failure clinic
83481	9N4w.00	Did not attend heart failure clinic
69062	9N6T.00	Referred by heart failure nurse specialist
32911	9Or..00	Heart failure monitoring administration
19380	9Or0.00	Heart failure review completed
90193	9Or1.00	Heart failure monitoring telephone invite

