In addition, the following CPRD-linked data will be used in this study:

- Hospital Episode Statistics (HES) Admitted Patient Care (HES APC) data
- HES Accident and Emergency (HES A&E) data
- Patient Level Index of Multiple Deprivation

HES APC data are collected on all admissions to National Health Service (NHS) hospitals in England. HES APC also covers admissions to independent sector providers (private or charitable hospitals) paid for by the NHS. HES APC does not cover accident and emergency (A&E, emergency department) attendances or outpatient bookings. In the financial year 2014/15 (April to March), 18,731,987 hospital episodes from 451 different NHS hospital trusts (known as ‘providers’) were recorded in HES APC. HES APC provides detailed clinical, demographic and organizational information for each Finished Consultant Episode. Data on drugs prescribed through hospital pharmacies to inpatients are not available in HES APC [[R18-0523](#)]. In this study, HES APC will be used to assess hospitalization (all-cause, respiratory disease related, or asthma or lower respiratory condition related) in the year prior to the index date among patients who were treated at English NHS health care providers. HES A&E data consist of individual records of patient care administered in the accident and emergency setting in England. These data are a subset of national A&E data collected by NHS England to monitor the national standard that 95% of patients attending A&E should wait no longer than 4 hours from arrival to admission, transfer or discharge. A&E data are submitted by A&E providers of all types in England. Data collected includes details about patients’ attendance, outcomes of attendance, waiting times, referral source, A&E diagnosis, A&E treatment (drugs prescribed not recorded), A&E investigations and Health Resource Group [[R18-0524](#)]. In this study, HES A&E will be used to ascertain A&E attendance for asthma or low respiratory conditions, which will be used to calculate the number of asthma exacerbation in the year prior to the index date.

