9.9 LIMITATIONS OF THE RESEARCH METHODS

The main analysis will exclude patients with other respiratory disease (e.g., COPD). This will exclude asthma-COPD overlap patients and some other patients and the results may not be representative to all asthma patients. However, Spiriva has both asthma and COPD indications. Therefore, for asthma-COPD overlap patients, the reason for initiating Spiriva Respimat can be unclear in existing data. Since the primary objective is to describe the characteristics of asthma patients prior to the initiation of Spiriva Respimat for the treatment of Asthma, it would be reasonable to exclude asthma-COPD overlap patients,

This study is based on existing data. It is possible that misclassification may happen for the measurement of comorbidities. However, we will use all the available data before the index date to minimize the possibility of misclassification.

Some covariates such as smoking status, alcohol use, BMI, pulmonary function, and eosinophil count may not be well recorded in CPRD. In the analyses we will present missing data as a separate category.

Some information may be recorded very infrequently or not at all in CPRD, e.g., number of people in a household, over-the-counter medication use, prescriptions in secondary care. These variables will not be assessed in this study.

The CPRD only includes patient data captured from general practitioners. Although some information about patient contacts with secondary care could be manually entered into the patient record, details about these specialty visits and hospital admissions (including dates, diagnoses, tests performed, length of stay) may be incomplete.

The CPRD may not be representative of all practices in the UK based on geography and size. There are certain patient groups that are missing from primary care records, such as prisoners, private patients, some residential homes and the homeless. Thus, selection bias cannot be ruled out. However, studies suggested that CPRD patients are broadly representative of the UK population in terms of age and sex. Patients are also comparable to the UK census in

terms of ethnicity, and comparable to the Health Survey for England for body mass index distribution in most patient subgroups.

The HES APC data and HES A&E data only have data for patients from England.

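### Both cardiac outcomes rest on GP Read codes alone although linked hospital diagnoses are available, so hospital-diagnosed cases may be missed and differences near the 10% cut-off may be misclassified

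*Protocol*

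**What the plan says.** Protocol 9.3.2.1 makes cardiac arrhythmia on the index date or in the year before it the primary outcome: "Cardiac arrhythmias is defined as having the following readcode in the above mentioned time period". Section 9.3.2.2 uses the same form for the secondary outcome: "Cardiac failure is defined as having the following readcode in the above mentioned time period". Each is followed by a closed list of GP codes, and neither has a hospital-diagnosis criterion.

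Section 9.4 names "Hospital Episode Statistics (HES) Admitted Patient Care (HES APC) data" among the linked sources and says "HES APC provides detailed clinical, demographic and organizational information for each Finished Consultant Episode". Its stated use is narrower: "HES APC will be used to assess hospitalization (all-cause, respiratory disease related, or asthma or lower respiratory condition related"), all in the prior year. No cardiac use is given.

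Section 9.9 says of secondary-care contacts in the GP record that "details about these specialty visits and hospital admissions (including dates, diagnoses, tests performed, length of stay) may be incomplete". It adds that HES covers England only. On misclassification of comorbidities it says: "However, we will use all the available data before the index date to minimize the possibility of misclassification".

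Section 9.7.1 compares the Spiriva Respimat group with each other group by ASD and treats 10% or more as meaningful.

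**The concern.** A patient admitted with atrial fibrillation or acute heart failure in the year before the index date counts as a case only if the practice entered a listed code in that year. Section 9.9 accepts that such entries may be missing and that their dates may be incomplete. With a one-year window, a wrong date can lose a case as surely as a missing diagnosis.

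The study already plans to use the linked data set that could show how often this happens. Classifying admissions as respiratory-related already needs clinical information on each episode, yet that information is not applied to either cardiac outcome. The ENCePP checklist (Annex 2, item 7.2.2) points to 9.9 for misclassification of endpoints. Section 9.9 discusses misclassification only for comorbidities, and 9.12 (Bias) reads None.

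At stake is the channelling conclusion. It is read against a fixed 10% line, and section 7 says the results can be used to choose propensity-score variables in later studies.

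**Working it through.** **The plan's own figure.** Table 1 (section 9.5) is the only precision statement. Wilson score intervals reproduce its n = 500 row exactly and 19 of its 20 cells; the exception is n = 2,000 at 10%, which gives 8.8–11.4 against the stated 8.8–11.3. Table 1 describes sampling error only. It neither addresses outcome misclassification nor is affected by this point.

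**Inputs.** The 10% cut-off is from section 9.7.1. The protocol gives no cardiac prevalence, capture rate or specificity, so every such value below is an assumption and a range is shown.

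**Formulas.** ASD = 100 × |p1 − p2| / √{[p1(1 − p1) + p2(1 − p2)] / 2}. Observed prevalence = sensitivity × p + (1 − specificity) × (1 − p).

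**Step 1: equal capture in both groups, perfect specificity.**

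| True prevalences | True ASD | Capture | Observed prevalences | Observed ASD | Crosses 10%? |
|---|---|---|---|---|---|
| 6% vs 3.5% | 0.025/0.2123 = 11.8 | 70% | 4.2% vs 2.45% | 0.0175/0.1791 = 9.8 | yes |
| 10% vs 7% | 10.8 | 80% | 8.0% vs 5.6% | 9.5 | yes |
| 8% vs 5% | 12.2 | 80% | 6.4% vs 4.0% | 10.8 | no |
| 8% vs 5% | 12.2 | 70% | 5.6% vs 3.5% | 10.1 | no |
| 8% vs 5% | 12.2 | 60% | 4.8% vs 3.0% | 9.3 | yes |
| 5% vs 2% | 16.4 | 70% | 3.5% vs 1.4% | 13.6 | no |

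At low prevalence the ASD shrinks by slightly more than the factor √capture. At 70% capture √0.7 = 0.837, so only true ASDs between 10 and about 12 (10/0.837 = 11.9) drop below the line.

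**Step 2: unequal capture (Spiriva group / comparator).**

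- True 7% vs 5%, ASD 8.4. At 90%/60% capture the observed 6.3% vs 3.0% gives 15.7. At 60%/90% the observed 4.2% vs 4.5% gives 1.5.
- True 5% vs 5%, ASD 0. At 90%/60% the observed 4.5% vs 3.0% gives 7.9.

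The error can therefore create, enlarge or hide a difference.

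**Step 3: imperfect specificity.** With sensitivity 0.8 and specificity 0.98, a true 5% is observed as 0.8 × 0.05 + 0.02 × 0.95 = 5.9%. Prevalence is then overstated despite missed cases.

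**Step 4: why HES should not simply be added for the whole cohort.** Suppose capture is 0.95 in linked and 0.70 in unlinked patients, and linkage is 70% in one group and 50% in the other. Average capture is 0.95 × 0.7 + 0.70 × 0.3 = 0.875 against 0.95 × 0.5 + 0.70 × 0.5 = 0.825. A true 5% in both groups is then observed as 4.375% vs 4.125%, an ASD of 1.2 where the truth is 0. Mixed ascertainment adds its own bias.

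**The case against.** A reader might infer that the cardiac prevalences and the ASDs are understated. The documents do not support that, for two reasons.

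- **Prevalence.** The lists include codes that do not establish disease, such as suspected heart failure, a heart failure screen, a screening invitation for high risk, and sinus arrhythmia. These push prevalence up, so the net direction is unknown.
- **ASDs.** Shrinkage towards zero needs equal under-recording. The study is looking for channelling and counts prior hospitalisation as a characteristic, so hospital contact, and with it under-recording, may well differ by group.

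Other points also stand. Section 9.4 says that key diagnoses and discharge data may reach the GP record. The lists contain follow-up codes (atrial fibrillation monitoring, heart failure clinic and review), so a hospital-diagnosed patient can qualify later without the discharge diagnosis being re-coded. The loss is only the remainder, of unknown size. Nothing in the protocol says how often these conditions are first diagnosed in hospital. The promise in 9.9 to use all available data concerns comorbidities, so it does not contradict 9.3.2. A Read-code definition applies uniformly across a UK cohort and is a defensible primary choice.

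One could add that a supporting definition can be left to an analysis plan. That carries less weight here: the protocol itself fixes the outcome lists and the use of HES APC, and as written they exclude hospital diagnoses.

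**Conclusion.** The point holds as possible under-ascertainment, not as a demonstrated understatement. The protocol defines both headline outcomes by GP codes, concedes that hospital diagnoses and dates may be incomplete there, and leaves the linked hospital diagnoses unused for those outcomes. Prevalence may be wrong in an unknown direction. ASDs may be biased towards zero under equal under-recording, or either way otherwise.

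The practical effect is confined to differences near the cut-off if capture is equal: at an assumed 70%, true ASDs of 10 to about 12 change class and larger ones keep theirs. Under unequal capture the movement can be larger (8.4 to 15.7 or to 1.5 in the assumed examples). All of these figures rest on assumed prevalences and capture rates. Because neither the size nor the direction of the error can be settled from the protocol, measuring it in the linked patients is worthwhile.

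**What to change.** Keep the Read-code outcomes for the full cohort. Add to 9.3.2.1 and 9.3.2.2, and to the stated use of HES APC in 9.4, a supporting definition restricted to HES-linked patients: a listed Read code, or an HES APC diagnosis of arrhythmia (respectively heart failure), on the index date or in the prior year. In that linked subset, report the prevalence and the ASDs under both definitions side by side, so that the reader sees whether any conclusion against the 10% line changes. Restricting both to linked patients avoids the mixed ascertainment shown in step 4.

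The cost is two hospital diagnosis code lists and one extra table. The linked subset is England only, and the protocol does not say how many of the 935 Spiriva Respimat patients it would hold, so its precision cannot be judged in advance. It is a supporting estimate, not a replacement. It addresses missed cases only and does not correct for listed codes that do not establish disease.
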